View	[name] CV	[name] CV Signed.pdf	0.01	10/20/2022 11:43 AM	[name]	CV/Biosketch	Yes
View	Basic Participant Information	BasicInformation.pdf	0.01	10/18/2022 3:38 PM	[name]	Research Measure	Yes
View	Screening Form	ScreeningForm.pdf	0.01	10/18/2022 3:37 PM	[name]	Research Measure	Yes
View	[name] CV	[name] CV.docx	0.01	9/12/2022 4:52 PM	[name]	CV/Biosketch	Yes

Study Population

1. * Provide the maximum number of individuals that

1. May participate in any study interaction or intervention (Including screening, consenting, and study activities)

AND/OR

2. You obtain any data/specimens about (regardless of identifiability)

at VCU and at other sites under the VCU IRB's oversight. See the help text for additional guidance.

100

2. If this is a multi-Center Project, what is the maximum anticipated number of subjects across all sites?

Not multi-center

3. * Provide justification for the sample size by explaining how you arrived at the expected number of participants and why this number is adequate for answering the research questions:

Our power estimates show that 28 or more measurements/surveys are needed to have a confidence level of 95% that the actual change in HRV d/t TENS unit use is within $\pm 5\%$ of our measurements of HRV. We estimate about a 30% compliance rate, so we arrived at 100 to account for dropouts and screen fails. We are not aiming to recruit an equal number of FGIDs/non-FGID, because our main aim is to figure out if the TENS unit improves vagal modulation in general, not to compare the degree of variability between FGID and non-FGID subjects.

4. * List the study inclusion criteria:

Female

12 – 21 years old

Either diagnosed OR not diagnosed with chronic idiopathic nausea, functional abdominal pain, dyspepsia and/or irritable bowel syndrome.

English speaking

5. * List the study exclusion criteria:

Patients who are unable to stand upright during the heart rate variability recording

Patients with a known bleeding disorder

Patients with swollen, infected, inflamed, or other skin eruptions on outer ear

Patients with epilepsy

Patients with any implanted cardiac pacemaker or defibrillator

Patients with serious arterial circulatory problems in the lower limbs

Patients with abdominal or inguinal hernia

Patients who are pregnant

Any unstable medical condition, such as renal disease, uncontrolled diabetes, etc.

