Week 0 Visit (Baseline): After the signing of the ICF, participants will take a pregnancy test. All other screening questions will have been answered previously in the REDCap Study Interest and Screening Form. If the pregnancy test is negative, the participant will be marked as eligible and assigned a Study ID. Participants will complete the GI Symptom Questionnaire on REDCap via a computer or tablet handed to the participant. Heart rate variability (HRV) will then be collected using a digital HRV device. These devices are commonly used to measure HRV, and this study will not be altering the use of that device for research purposes. To measure HRV, electrode leads connected to the device will be placed on the participant's chest and stomach while they are laying down. HRV will be measured for 15 minutes of supine time and 5 minutes of standing time. Participants will then be hooked up to the TENS microcurrent unit (the unit has a pulse rate from 0.1 - 150 Hz, a pulse width of 2 - 200 mS, and an adjustable pulse amplitude of 0-0.7 mA peak at 1000 ohms- the unit will be set at a pulse rate of 50 and a pulse width of 5ms. The mA will be turned up just until the participant can feel it, and then back down to where they can just not feel it, so specific mA strengths may vary between each participant and session), and heart rate variability will be measured again (supine) for another 30 minutes. The unit will be disconnected and HRV will then again be measured for 15 minutes of supine time and 5 minutes of standing time. The HRV device will continuously measure and the electrodes will not be taken off/the machine will not be turned off in between physical positions and conditions since it gives us information on HRV during episodes of position change. Measurement times, including the start time, time when the participant changes physical position, and end time will be recorded in REDcap. Upon completion of the study visit, HRV data from the device will be exported into software-compatible files on a VCU managed computer. They will then be stored on a VCU managed drive with their Study ID and name of the visit (baseline/follow up) as the title of the file for later use in Kubios, an HRV analysis software. The files generated by the HRV measurement devices include information such as the measurement start and end times and the participants' interbeat intervals (IBI/RR)/ECG during the measurement. Files with this information will only be stored in Kubios and/or the VCU drive until analysis is complete. Following the completion of the HRV measurement, the participant will receive a printout of instructions and a physical demonstration on how to use the unit by an approved study team member and instructed to use it at a consistent time each day for 2 hours daily over 4 weeks. The participant doesn't have to hold the unit the entire time, as long as their ear clip is connected to them and that clip is connected to the machine, they have the freedom to set down the unit near them, hold it, put it in a pocket, or use the belt clip on the device. The ear clip connects to the unit by a cord. The participant will be asked to complete the TENS Microcurrent Unit Daily Recording Diary to document when the device was used and where on their ear, as well as the times of starting/ending sessions. Participants will be emailed daily via REDcap survey distribution for completion. The study coordinator will contact the patient 2 times over the 4 weeks to check in for adverse events that would be promptly recorded and reported and to remind them to keep using the device, but a coordinator contact will be on the instructions printout should they need to report any AEs/device issues prior to the check-in. Problems may also be reported on the daily recording diary, upon which study team members will receive a notification. The next visit will be scheduled, and payment will be processed.

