
Week 4 Visit: The participant and parent(s)/guardian(s) if applicable, will return to the FGID clinic or PRU and complete heart rate variability measuring using the same procedures as at baseline, return their TENS microcurrent unit, complete the same symptom questionnaire, and return their daily recording diaries if done on paper. Payment will be processed.

3.

Tests: Heart Rate Variability assessment, pregnancy test during screening

Interventions: TENS microcurrent unit usage

Measures: Daily recording diary, GI symptom questionnaire

8. * The IRB only reviews research activities, so indicate for each of the study activities described in the question above or in the protocol which activities are:

- Being performed exclusively for research purposes (i.e. they would not otherwise be done apart from this study) **VERSUS**.
 - Alterations of routine activities/procedures (e.g. the study is altering the timing, frequency, method, location, amount, etc.) **VERSUS**.
 - Being done for other purposes and whose data/results will be used secondarily in the study (e.g. standard medical or psychological tests, routine education practices, quality improvement initiatives, etc.).
- See the help text for additional guidance

All research activities are being performed exclusively for research purposes.

9. If applicable, describe alternatives (research or non-research) that are available to potential participants if they choose not to participate in this study:

No alternatives will be available to potential participants. Participants will be notified that declining to participate will not impact their clinical care and that their participation is totally voluntary.

10. Upload any supporting tables or documents (e.g. protocol documents, figures/tables, data collection forms, study communications/reminders):

Upload ALL instruments/guides that will be used or that participants will experience (i.e. see, hear, complete), including measures, scripts/questions to guide interviews, surveys, questionnaires, observational guides, etc.:

Upload ALL recruitment and screening materials, including such as ads, flyers, telephone or in-person scripts, letters, email invitations, TelegRAM announcements, and postcard reminders, screening scripts, screening forms, and screening measures:

	Document Name	Document	Version	Date Modified	Uploaded By	Type	Approved

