2. * Describe how data will be linked or unlinked to identifiers including email addresses, names, and/or IP address.

REDCap Study Interest & Screening Forms will contain names, phone numbers, and emails if this information is provided by the potential participant.

REDCap daily diary forms will be linked to a separate form with identifying/contact information (name, email, phone number) in the participant's REDCap record. None of the daily recording diary response forms require the input of personal information, but we ask for their initials for consistency and tracking. Symptom questionnaire will be linked in the same way.

3. * How will you protect your data collection from fraudulent responses:

The REDCap Study Interest & Screening Form will have a reCAPTCHA test enabled to protect the form link from fraudulent responses.

Daily recording diaries will be sent out individually to each participant. Each daily form will have a unique access URL, and once it is completed the answers cannot be changed. Participants will be encouraged to give honest answers on the form, and even if they did not use it we still would like that information to take into account. Symptom questionnaires will be given to the participant via a REDCap survey at their in-person visits via a VCU-managed computer or with the survey link opened on a tablet. These questions are not particularly sensitive or difficult to answer, so we will communicate the importance of honesty, but no survey questions are required.

4. * Is there an alternative method for completion of the data collection other than the internet?

- Yes
 No

5. * If yes, describe the alternative(s).

Participants can choose to take home paper printouts of the daily diary REDCap form that they can write on and return to study staff at the final in-person visit. They may also choose to be verbally administered questionnaire items by study staff if requested.

6. * Describe how individuals will be able to skip or not answer particular questions. If any questions are mandatory, provide justification.

We will encourage participants to fill out their diaries accurately, honestly, and consistently. Participants may skip any questions they would like, but because the diary and symptom questionnaires are so short, objective, simple, and do not cover any particularly sensitive material, we will encourage them not to skip if possible.

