Other protection not listed in this question – describe below

N/A – no email/online communications

6. Specify any other places where this study's paper and electronic research data and/or physical specimens will be stored and any other ways they will be secured from improper use and disclosure.

See the help text for additional guidance.

Paper diary documents will be copied into the corresponding REDcap forms for the participant and immediately shredded upon entry and verification.

Pregnancy test strips and urine samples will be immediately disposed of after reading.

The TENS unit does not record or store data.

7. * If research data/specimens will be sent/released to person(s) or group(s) outside of the VCU study team or the PI's department for the conduct of this protocol (not for future sharing),

1) identify the data/specimen recipient(s) along with their VCU department or other institutional or organizational affiliation(s).

2) give a description of what identifiers and/or codes will accompany the data/specimens.

If data/specimens are not being sent/released outside of the VCU study team or the PI's department, state that:

N/A

8. * Select all identifiers that will be collected at any time as part of this study (including for recruitment, data gathering, data analysis, etc.), even if the data will eventually be anonymized:

Names

Geographic Locators Below State Level

Social Security Numbers

Dates (year alone is not an identifier)

Ages over 89 (age under 89 is not an identifier)

Phone Numbers

Facsimile Numbers

E-mail Addresses

Medical Record Numbers

Device Identifiers

Biometric Identifiers

Web URLs

IP Addresses

Account Numbers

- Health Plan Numbers
- Full Face Photos or Comparable Images
- License/Certification Numbers
- Vehicle ID Numbers
- Other Unique Identifier
- No Identifiers
- Employee V#

9. * If the study will code (i.e. de-identify) the research data by replacing subjects' names and/or other identifiers with assigned subject IDs, explain the following aspects of the coding process:

- **The process for how subject IDs will be generated/assigned (e.g. random, sequential)**
- **Whether there will be a key that links the subject ID with direct identifiers. If there will be no linkage key, state that.**

If a key will be created, describe

- **The place where the key will be stored**
- **The role(s) of all individuals who will have access to the key**
- **When the key will be destroyed**

See the help text for guidance.

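### The diary's problem alert cannot work for participants who keep the diary on paper, because the sheets come back only at Week 4

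*Protocol*

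**What the plan says.** The Week 0 description under Study Procedures, question 7, sets the diary up as an online form: "Participants will be emailed daily via REDcap survey distribution for completion". The same paragraph gives it a safety function, with no exception for format: "Problems may also be reported on the daily recording diary, upon which study team members will receive a notification".

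Three other places deal with paper:

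- Active Internet Data Collection, question 5, lets a participant "take home paper printouts of the daily diary REDCap form that they can write on and return to study staff at the final in-person visit".
- The Week 4 Visit description has participants "return their daily recording diaries if done on paper".
- Data Confidentiality and Storage, question 6, says: "Paper diary documents will be copied into the corresponding REDcap forms for the participant and immediately shredded upon entry and verification".

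Two further safety routes do not depend on the diary format. The Week 0 description says: "The study coordinator will contact the patient 2 times over the 4 weeks to check in for adverse events". It also puts a coordinator contact on the instruction sheet for problems arising before a check-in. Under Risks, Discomforts, Potential Harms and Monitoring, question 4, the coordinator asks about ear irritation at those check-ins, and the instruction to stop using the unit when irritation or scabbing is severe is given in that context.

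**The concern.** The notification statement is unqualified, but for a paper user nothing in the plan could produce the notification during home use. Someone who writes a problem on the sheet may reasonably think that she has reported it, and participants can be as young as 12. Skin irritation and scabbing of the ear are among the few physical risks that the protocol names, and they would arise during unsupervised use at home. At stake is whether a written problem reaches staff while it can still be acted on. If it does not, one of the three reporting routes described is missing for part of the sample, and the plan does not say so.

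**Working it through.** No sample size, power or error rate is involved. The check is a comparison of the sections plus simple arithmetic on the exposure schedule.

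**1. Path of an online entry.** The survey is emailed daily, the participant completes it in REDCap, and the team is notified. Notice comes during the period of use.

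**2. Path of a paper entry.** The participant writes on a sheet at home, hands it in at the Week 4 visit, and staff copy it into REDCap. The first point at which staff can see the entry through the diary is the return visit. The protocol describes no interim collection, photograph, upload or telephone relay of paper sheets. That the alert works only online is an inference from this workflow, since the protocol does not say so in words. But it gives no means by which a sheet held at home could notify anyone.

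**3. Longest delay.** Participants are "instructed to use it at a consistent time each day for 2 hours daily over 4 weeks".

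- Days from first home use to return: 4 weeks × 7 = 28 days.
- Scheduled home use in that time: 2 hours × 28 = 56 hours.

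A problem written on the first day may thus go unread for about 28 days and up to 56 scheduled hours. A problem written near the end waits only until the visit, so 28 days is the maximum and not the typical delay.

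**4. Entries never seen.** The only stated return point for paper is the Week 4 visit. Under question 5 of the risks section, participants who cannot wear the unit because of discomfort or severe irritation are withdrawn, and no step is given for recovering a withdrawn participant's paper diary. Such an entry may never be read.

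**5. How many people.** The share of device users affected is the share who choose paper multiplied by the share of those whose diary is not returned. The document gives neither. The nearest figure is in Study Population, question 3: "We estimate about a 30% compliance rate". It is offered to cover dropouts and screen failures together. Screen failures receive no unit and no diary, so the figure does not give the return rate among device users.

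**6. What remains for paper users.** The two check-ins and the printed contact both operate during the 4 weeks. The delay in step 3 therefore applies to the written entry and not necessarily to the adverse event itself.

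**The case against.** The strongest reply is that the diary is only a supplementary route. The Week 0 description names the two check-ins and the printed contact first, and those cover every participant whatever the diary format. The stop instruction for severe irritation is tied to the check-in question and not to the diary. The device is designated non-significant risk. The diary form and instruction sheet are listed but not shown, and may already tell paper users to call. All of this stands, and it limits the point. It does not remove the mismatch: the protocol text promises a notification that its own paper procedure cannot deliver, and it would need reconciling even if the form carries a warning.

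A reader might infer more than the document supports:

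- **That paper users have no safety follow-up.** They have the same check-ins and the same contact as online users.
- **That about 70% of paper diaries would be lost, taking 1 − 0.30.** The 30% mixes in screen failures. There are also reasons to return: the unit is handed back at Week 4, and $75 of the $100 payment follows that visit.
- **That online records are complete and only paper records are not.** Questions may be skipped online, and someone who stops using the unit can also stop opening the emailed surveys. The online advantage is promptness.
- **That a reported irritation rate would be biased.** The stated aim concerns heart rate variability, and the protocol proposes no estimate of an irritation rate.

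**Conclusion.** The point holds in limited form. The notification statement in the Week 0 description conflicts with the paper procedure in the Week 4 description, the Active Internet Data Collection section and the Data Confidentiality section. A problem written on paper reaches staff through the diary up to about 28 days later, or not at all if the diary is not returned. This rests on two readings: that the alert depends on a REDCap entry, and that no unshown document provides an interim relay. The number of participants affected cannot be derived. Because two other routes remain open to paper users, this is a minor to moderate gap in one safety-reporting route. It does not affect the sample size or the analysis of heart rate variability. It is worth correcting because the correction is cheap and participants, including minors, use the unit at home.

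**What to change.** Reconcile the Week 0 and Week 4 descriptions with Active Internet Data Collection, question 5, in three steps:

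1. State that the notification applies to diary entries made online, and that the paper diary is not a route for reporting problems.
2. Print on the paper form that any problem must be phoned or emailed to the coordinator the same day.
3. At each of the two check-ins already planned, have the coordinator ask paper users about any problems written in the diary to date, and record them in REDCap then.

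The cost is a protocol amendment, one line on the form and a few extra minutes per call for paper users. No extra contacts and no change to their timing are needed. Return by post is not proposed, because the Privacy section marks mailing of materials to or from participants as not applicable.

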****The IRB will expect studies to operationalize all selected checkboxes into the conduct of the research.**

To elaborate on any response, also click the "Other Protections" checkbox to provide further explanation in the last free-text question.

Read the entire page before filling out the form.

1. * Protections when conducting one-on-one in-person interventions or interactions (for groups see Q2 below):

- Conducting study activities in locations that maximize privacy (limited people around, closing doors, drawing drapes around beds, monitoring voice volume, etc.)**
- Verifying identity before discussing personal information.**
- Asking the participant if they are comfortable answering questions in that location**
- Asking the participant if they are comfortable with having other people present (if any)
- Moving away from other people when conducting activities in public spaces or offering a private space
- Offering other options of ways to respond to sensitive questions (i.e. pointing, clicking, or writing) if uncomfortable verbally responding
- Using generic signs on research rooms and spaces, particularly for research on stigmatizing or sensitive topics**
- Other protections not listed in this question – describe below
- N/A – study has no in-person interventions or interactions with participants

2. * Protections when conducting group interventions or interactions:

- Conducting study activities in locations that maximize privacy (limited people passing by, closing doors, monitoring voice volume, etc.)
- Moving to a more private area to answer questions or to discuss concerns
- Discussing privacy with the participants and the importance of not talking outside the group about what other people say during the group session
- Allowing participants to use a pseudonym or limiting use of individuals' names during the group activity
- Asking everyone in a public group setting (e.g. classrooms, workshops) to turn something in (blank or filled) so participants do not have to self-identify when turning in materials
- Collecting paper forms in a closed box or envelope rather than passing to others or leaving in an open area
- Limiting participant identifiers that would be visible on paper documents (i.e. using study IDs instead of direct identifiers)
- Allowing people to distance themselves from other participants during group activities

- Offering other options of ways to respond to sensitive questions (i.e. pointing, clicking, or writing instead of speaking)
- Using generic signs on research rooms and spaces, particularly for research on stigmatizing or sensitive topics
- Ensuring non-participating individuals are not captured on recordings or in photos
- Other protections not listed in this question – describe below
- N/A – study has no group interventions or interactions**

3. * Protections when conducting remote interventions or interactions (e.g. phone, text, email, video-conference, tele-health, online, etc.):

- Conducting study activities in locations where study staff can maximize their own privacy (limited people around, closing doors, monitoring voice volume, etc.)**
- Leaving/sending generic messages that avoid using study and participant identifiers, such as names, study titles, clinics, study topics, etc.**
- Obtaining permission prior to sending text messages**
- Advising the participant to move to a location where they are comfortable answering questions and will not be overheard - incorporate this instruction into your study materials**
- Advising online participants to complete the activity at a time and location where they will be comfortable answering questions - incorporate this instruction into your study materials
- Ensuring non-participating individuals are not captured on recordings or in photos
- Offering other options of ways to complete the activity (i.e. online, paper, phone) if more privacy is desired
- Offering a way to save and return later to the online activity if privacy is compromised
- Other protections not listed in this question – describe below
- N/A – study has no remote interventions or interactions with participants

4. * Protections when mailing study materials to/from participants:

- Obtaining permission to mail study materials
- Confirming/verifying the accuracy of addresses before mailing items
- Ensuring the participant is able to personally receive mailed materials and has a way to protect their own privacy if they do not want others to know they are receiving research communications (i.e. notifying participants of when to expect it)
- Using return address labels and document headers that avoid study identifiers, such as study names, clinics, study topics, etc.
- Avoiding or limiting use of participant identifiers and health information on mailed documents (i.e. using study IDs instead of direct identifiers)
- Providing a return mailing address label or pre-addressed envelope to ensure returned items are sent to the correct address
- Communicating receipt of mail from participants and/or asking them to notify you when they mail it to ensure study documents are not lost in transfer
- Offering other options of ways to complete the activity (i.e. by phone or online) if desired
- Other protections not listed in this question – describe below
- N/A – not mailing any materials to/from participants**

5. * Protections when analyzing or disseminating study data *Applicable to all studies*:

- Working only in locations where the study team can ensure privacy (not working in close proximity to non-study personnel, closing doors, closing/putting away documents/files before leaving, etc.)**
- Securing physical materials only in locations that ensure privacy (access limited to authorized study personnel)**
- Obtaining explicit parental permission before disseminating or sharing recordings or photos of children
- Blurring/redacting/hiding faces and other identifiable features/marks (tattoos, scars, birthmarks, distinctive voice, etc.) in recordings or photos prior to disseminating or sharing
- Only publishing or presenting aggregate results or findings (i.e. no individual-level information)**
- Taking additional steps to protect participant identities when publishing or presenting individual-level information, quotations, results, images – describe below

Other protections not listed in this question – describe below

6. Describe any other way(s) that the research team will protect participants' privacy. See *the help text for additional guidance.*

We will be using a secure REDcap database and OnCore to store data. The eligibility screening form/consent form will have the participants' name and will be stored in a binder in a locked cabinet separate from the participant's study data, which will only have a study ID on it. REDcap data forms will be stored in a separate form than the forms with participants' name and eligibility information. The heart rate variability assessment will be in a private room. The HRV measurements will be stored with no identifiers. The data collection diaries will have no identifiable information on them. The TENS unit poses no privacy risks as it does not collect data or personal information.

Data Confidentiality and Storage

Confidentiality refers to the way private, identifiable information about a participant or defined community is maintained and shared. It describes how the study's research materials (data, specimens, records, etc.) are protected from unauthorized access.

Instructions for this page:

Select all the ways that the research team will keep the study materials and data confidential throughout the course of the study. Not all will be applicable to every study.

To elaborate on any response, also click the "Other Protections" checkbox to provide further explanation in the last free-text question.

Read the entire page before filling out the form.

1. * Protections for paper research materials:

- Maintaining control of paper documents at all times, including when at an off-campus location
- Limiting or avoiding use of participant identifiers on paper documents (i.e. using study IDs instead of direct identifiers)
- Storing paper documents in a secure location accessible only to authorized study personnel
- Promptly transcribing, scanning, or abstracting data from paper into electronic platforms with destruction of the paper copy
- Proper destruction of paper records (and obtaining prior permission when required) in accordance with VCU Records Management policies
- Other protection not listed in this question – describe below
- N/A – no paper research materials

2. * Protections for research specimens:

- Maintaining control of specimens at all times, including when at an off-campus location
- Storing specimens in a secure location accessible only to authorized study personnel
- Labeling specimens with subject ID or other coded information instead of direct identifiers
- Final destruction of specimens will be in accordance with VCU policies and specimen containers will be devoid of any identifiable information
- Other protection not listed in this question – describe below
- N/A – no research specimens

3. * Protections for electronic files/data - See <https://ts.vcu.edu/about-us/information-security/data-management-system/>

- *Required for all studies* Use VCU-approved methods of data storage, transmission, and transfer (see <https://dms.vcu.edu>)
- Remotely accessing VCU network storage to store data when at off-campus locations
- Ensuring unauthorized individuals who might share a device do not have access to study materials (e.g. individual logins, separate accounts)
- Using VCU-approved data collection tools and apps (e.g. REDCap) and storing exported analysis files in VCU-approved storage locations (see <https://dms.vcu.edu>)
When using non-VCU-approved electronic data collection tools, storage locations, data transfer platforms, and mobile apps (e.g. Dropbox, Box, Survey Monkey, Fitbits, novel apps, multi-site data collection platforms):
- consulting with VCU Information Security on proper data management (see <https://ts.vcu.edu/askit/essential-computing/information-security/>);
• advising participants about the terms of use and privacy policies of those sites/apps;
• limiting or avoiding use of identifiers; and
• removing data promptly from the external location after transferring it to a VCU storage location
- De-identifying the research data by replacing subjects' names with assigned subject IDs
- Storing the study's linkage key in a password-protected and VCU-approved storage location (see <https://dms.vcu.edu>)
- When analyzing particularly sensitive information, using computers that are unconnected from the internet.

Proper destruction of electronic records (and obtaining prior permission when required) in accordance with VCU Records Management policies

Other protection not listed in this question – describe below

4. * Protections for computers and research devices/apps that are provided to participants for use in the study and taken out of the lab (i.e., giving participants a phone or iPad to take home, wearable trackers, apps, etc.):

Transferring data promptly from the device/app given to the participant to a VCU storage location

Setting strong passwords on computers and research devices (when applicable) that leave VCU with participants

Device/app set up by VCU Information Security

When providing devices or mobile apps to children, informing parents about the settings and how to manage them (if applicable), internet access, and any other installed apps on the device

Other protection not listed in this question – describe the device/app and protection below

N/A – no computers or devices/apps being provided for participant use outside the lab

5. * Protections for email/online communications

Only using VCU/VCU Health email addresses for study-related communications

Only using VCU/VCU Health–approved methods of teleconferencing or video conferencing (e.g. Zoom) (for studies involving HIPAA, contact VCU or VCU Health Information Security [as appropriate] about HIPAA-compliant systems)

Other protection not listed in this question – describe below

N/A – no email/online communications

6. Specify any other places where this study's paper and electronic research data and/or physical specimens will be stored and any other ways they will be secured from improper use and disclosure.

See the help text for additional guidance.

Paper diary documents will be copied into the corresponding REDcap forms for the participant and immediately shredded upon entry and verification.

Pregnancy test strips and urine samples will be immediately disposed of after reading.

The TENS unit does not record or store data.

7. * If research data/specimens will be sent/released to person(s) or group(s) outside of the VCU study team or the PI's department for the conduct of this protocol (not for future sharing),

1) identify the data/specimen recipient(s) along with their VCU department or other institutional or organizational affiliation(s).

2) give a description of what identifiers and/or codes will accompany the data/specimens.

If data/specimens are not being sent/released outside of the VCU study team or the PI's department, state that:

N/A

8. * Select all identifiers that will be collected at any time as part of this study (including for recruitment, data gathering, data analysis, etc.), even if the data will eventually be anonymized:

Names

Geographic Locators Below State Level

Social Security Numbers

Dates (year alone is not an identifier)

Ages over 89 (age under 89 is not an identifier)

Phone Numbers

Facsimile Numbers

E-mail Addresses

Medical Record Numbers

Device Identifiers

Biometric Identifiers

Web URLs

IP Addresses

Account Numbers

- Health Plan Numbers
- Full Face Photos or Comparable Images
- License/Certification Numbers
- Vehicle ID Numbers
- Other Unique Identifier
- No Identifiers
- Employee V#

9. * If the study will code (i.e. de-identify) the research data by replacing subjects' names and/or other identifiers with assigned subject IDs, explain the following aspects of the coding process:

- **The process for how subject IDs will be generated/assigned (e.g. random, sequential)**
- **Whether there will be a key that links the subject ID with direct identifiers. If there will be no linkage key, state that.**

If a key will be created, describe

- **The place where the key will be stored**
- **The role(s) of all individuals who will have access to the key**
- **When the key will be destroyed**

See the help text for guidance.

Study IDs will be generated sequentially in REDcap. A key with participant identifiers will be stored in a separate form in REDcap. Only approved research personnel will be able to access this key. This key will be stored until the study is closed. Some participants will give us permission to use their contact information to contact them for future studies. We will not keep the code key or any link to the data from this study upon its closing, but we will be keeping a separate, unlinked list of names and contact info for those who consent to contact for future studies.

Data Retention

1. * **Select all of the ways that individually identifiable information obtained during pre-screening and/or screening will be handled for individuals who DO NOT qualify for the study:**

- N/A - study does not require screening procedures
- Immediately destroy the information and identifiers (no data collected)
- Immediately destroy the identifiers connected with the data (anonymization)
- Store until the end of study & then destroy
- Use as "screening failure" data by members of the study team**
- Provide to others outside of the research team (with the participant's permission)
- Request permission from participant to maintain and use the identifiable information
- Other

2. * **Will participants be able to withdraw their data (paper, electronic, or specimens) from the study (e.g. ask that it be destroyed or returned) if they no longer wish to participate? (FDA-regulated studies should select No – see help text)**

- Yes
- No**

3. * **What will happen to the research materials (e.g. data, specimens, documents, etc.) when the research has been completed?**

- Stored indefinitely with identifiers removed**
- Stored indefinitely with identifiers attached
- Destroyed at the end of study once the minimum time required for data retention has been met per VCU Data Retention Policy and/or sponsor retention requirements
- Destroyed when notified by sponsor but not less than the minimum time required for data retention per VCU Data Retention Policy
- Other

Sharing Plan

This page addresses times when investigators may be required to share information about participants or may desire to share their research information/specimens with the aim of advancing science. This page creates a plan for when and how information/specimens could be shared.

